## **7.5 Discharge**

Discharge is the actual date and time the subject is discharged. For subjects discharged within 48 hours of exiting the procedure room, it is not required to repeat tests collected during the Post-Procedure period that are also required for the discharge visit. If the subject was discharged over a weekend or holiday, the discharge assessments may be completed on the last weekday prior to discharge.

The following assessments will be conducted within 24 hours of the date and time of discharge.

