### 8.3 AE Reporting Requirements

All AEs will be captured from the time of enrollment until subject participation has ended (i.e. completion of study or discontinuation). See section 8.3.1 for events that are not required to be reported to Edwards.

Pre-existing medical conditions or symptoms reported prior to subject enrollment will not be recorded as an AE. In the event there is a worsening in the pre-existing medical condition or symptoms due to the device or study-related procedure, then an AE must be recorded.

Death should not be recorded as an AE, but should be reflected as an outcome to another specific AE.

If known, the diagnosis for an AE should be recorded, rather than listing individual signs and symptoms.

All AEs will be reported in subject medical records, and the appropriate eCRF throughout the duration of the study, and will be followed until resolution, stabilization or study completion.

All SAEs and Device Deficiencies that might have led to a SAE should be reported to Edwards immediately, but not later than 3 calendar days after site study personnel's awareness of the event.

Other AEs must be reported to Edwards as soon as practical but no later than 10 working days of awareness.

Information must be entered into the electronic database or, when the electronic database is not available, reported directly to the Edwards Safety Officer. In the event that the EDC system is not in service, a paper copy of the AE CRF must be e-mailed to [contact] according to the timelines described above.

At the time of initial AE notification, the following minimal information must be provided:

- Subject ID
- AE term/diagnosis
- AE onset date

For selected events, the site might be requested to provide to Edwards (or designee) a copy of

anonymized supporting documentation (such as hospital record, laboratory results, autopsy results).

All AEs will be reviewed by the Edwards Safety Officer. Each AE will be assessed as to its relationship to the study device and/or implant procedure, whether it was anticipated or not anticipated, and whether it qualifies as an SAE and USADE.

Depending on the local requirements or following agreement between both parties, Edwards or the Principal Investigator will be responsible for performing safety reporting to the EC according to the relevant local regulatory requirements.

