### **8.3.1 Events that do not require reporting to Edwards**

For purposes of this study, the following events will not be required to be reported as AEs to Edwards, because they are normally expected to occur in conjunction with transcatheter valve implantation or are associated with customary, standard care of subjects undergoing THV implantation:

- Post-operative pain.
- Post-anesthesia emesis, nausea or headache (within 24 hours of procedure).
- Electrolyte imbalance without clinical sequelae following procedure, even if requiring correction.
- Low grade temperature increase ( $\leq 101^{\circ}\text{F}$  or  $38.5^{\circ}\text{C}$ ).
- Elevated white blood count, outside the standard laboratory normal value, without signs and symptoms of infection.
- Minor, localized tenderness, swelling, induration, oozing, etc. at incision / delivery system insertion site.
- Systolic or diastolic blood pressure changes that do not require treatment or intervention.
- Thrombocytopenia: does not become an AE until treatment is administered; Suspected heparin-induced thrombocytopenia should be reported.
- Hyperglycemia – The use of insulin in the post-operative period does not constitute hyperglycemia if during the index hospitalization. An elevated blood sugar of less than 250 mg/dL during the first 48 hours post-operative does not constitute hyperglycemia.
- Expected, non-clinically significant events such as non-significant lab variances.
- Dizziness: imprecise term commonly used to describe various symptoms such as faintness, giddiness, imbalance, lightheadedness, unsteadiness or vertigo without signs of TIA or stroke.

Additionally, pre-planned future surgical procedures not associated with the study procedure or device do not need to be reported.

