## APPENDIX B. DEFINITIONS

Term	Definition	Reference/ Justification
Access Site	Any location (arterial or venous) traversed by a guidewire, a catheter or a sheath for TAVR	VARC-1 (23)
Access Site Related Complication	Any adverse clinical consequence possibly associated with any of the access sites used during the procedure Planned repair of access site entry portals are not considered access site-related complications.	VARC-1, VARC-2 (24)
Acute Kidney Injury (AKI)	AKI is defined by an abrupt decrease in kidney function 
 
Reportable AKI is for any creatinine with an increase in serum creatinine to > 150% of baseline, OR
 
increase of <math>\geq 0.3</math> mg/dL compared to baseline within 48 hours of index procedure, OR
 
Urine output < 0.5 mL/kg per hour for > 6 but < 12 hours
 
 Patients receiving renal replacement therapy (dialysis, hemodialysis, peritoneal dialysis, hemofiltration, transplant therapy) are considered to meet Stage 3 AKI criteria. For AKI diagnosis beyond Index Procedure (or for subjects who do not get Index Procedure), the same criteria are to be used with a pre-AKI diagnosis baseline. Note: AKI stage will be determined per VARC-2 criteria.	AKIN / KDIGO / VARC-2 / Sponsor
Angina / Cardiac Chest Pain	Chest pain due to myocardial ischemia caused by an imbalance between myocardial blood supply and oxygen demand.	Sponsor
Aortic Dissection	Aortic dissection is defined as separation of the layers within the aortic wall. Tears in the intimal layer could have blood entering intima-media space resulting in the propagation of dissection (proximally or distally).	Sponsor
Aortic Stenosis, Native	Aortic stenosis is classified as "severe" when the following are present: 
 
Jet velocity <math>\geq 4.0</math> m/s
 
Mean gradient <math>\geq 40</math> mmHg
 
Valve area <math>\leq 1.0</math> cm^2
 
Valve area index <math>\leq 0.6</math> cm^2/m^2
 
	2014 AHA/ACC

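### The urine-output limb of the reportable-AKI definition stops at 12 hours, so longer oliguria can be left out of the AKI count where it is the only qualifying evidence

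*Combined protocol and SAP*

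**What the plan says.** The Acute Kidney Injury entry in Appendix B (Definitions) gives three criteria joined by OR:

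- Creatinine, relative: "Reportable AKI is for any creatinine with an increase in serum creatinine to > 150% of baseline, OR"
- Creatinine, absolute: a rise of at least 0.3 "mg/dL compared to baseline within 48 hours of index procedure, OR"
- Urine output: "Urine output < 0.5 mL/kg per hour for > 6 but < 12 hours"

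Subjects on renal replacement therapy "are considered to meet Stage 3 AKI criteria". For AKI after the index procedure, or in subjects who never have it, the same criteria apply against a pre-AKI baseline. The entry ends: "Note: AKI stage will be determined per VARC-2 criteria". The stage thresholds themselves are not printed.

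Three other places bear on the point:

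- Section 8.3: "All AEs will be captured from the time of enrollment until subject participation has ended".
- Section 8.3.1, introducing its exemptions: "the following events will not be required to be reported as AEs to Edwards". Neither AKI nor low urine output is on that list.
- Section 7.5, for subjects discharged within 48 hours of leaving the procedure room: "it is not required to repeat tests collected during the Post-Procedure period that are also required for the discharge visit".

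**The concern.** A threshold for reporting an injury should stay met as the injury goes on. Neither creatinine criterion has a ceiling on the size of the rise. The urine criterion does have a ceiling, on duration, so the same deficit stops qualifying once it has lasted 12 hours.

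At stake is the completeness and consistency of one safety count in a study whose objective includes confirming procedural safety. Renal insufficiency and renal failure are listed procedural risks (Section 9.2). AKI is also one of the complications that Appendix B names under valve procedure-related rehospitalization. Because the same criteria are carried past the index procedure, the ceiling applies throughout follow-up.

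**Working it through.** The plan gives no figure to reproduce here. The check reads the definition as a logical rule and then looks for any other text that would close the gap.

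**Step 1: the urine criterion as a rule.** Inputs, from Appendix B: rate below 0.5 mL/kg per hour; duration D in hours. The criterion is met if the rate is below 0.5 and 6 < D < 12. With the rate below 0.5 throughout:

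| Duration of low output | Criterion as printed | Without the upper limit (D > 6) |
|---|---|---|
| 6 h | not met | not met |
| 7 h | met | met |
| 11.9 h | met | met |
| 12 h | not met | met |
| 14 h | not met | met |
| 24 h | not met | met |

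As printed, the answer changes from met to not met at 12 hours with no improvement in the subject.

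**Step 2: other routes to the AKI label.** There are three.

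- Creatinine above 150% of baseline.
- A creatinine rise of at least 0.3 mg/dL within 48 hours of the index procedure.
- Renal replacement therapy.

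A subject with 12 hours or more of low output who meets none of these meets no listed criterion.

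**Step 3: how far creatinine covers the gap.** Table 3 schedules creatinine at screening, post-procedure (the 48 hours after leaving the procedure room, Section 7.4) and discharge (Section 7.5). None is scheduled later. Subjects who stay beyond 48 hours therefore have a second post-implant value at discharge. Those who leave sooner may have only one, because Section 7.5 waives the repeat. Creatinine will often catch the case, but the schedule does not guarantee it.

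**Step 4: the staging note.** The three criteria decide whether an event is reportable AKI; the note decides how AKI is staged. The note does not alter the printed threshold, and without the stage thresholds a site has only the three criteria to apply.

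**Step 5: the general adverse-event rules.** Section 8.1 defines an adverse event as any untoward medical occurrence. Section 8.3 requires all of them to be captured, and Section 8.3.1 does not exempt oliguria. The event is therefore recorded. However, Section 8.3 prefers a known diagnosis to individual signs and symptoms. A site that applies Appendix B literally could conclude that AKI is not met and enter a sign or a different diagnosis. The event is then outside the AKI count and may not be staged.

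**Step 6: number affected.** Urine output appears in no visit list and not in Table 3, so this criterion works only from routine clinical records. No count or rate can be derived.

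**The case against.** The strongest reply is that the wording does little harm, and much of that reply stands.

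- *Nothing goes unreported.* A reader might infer that prolonged oliguria could escape reporting altogether. The documents do not support that: Sections 8.1, 8.3 and 8.3.1 together keep it reportable as an adverse event. If it led to death, it would be a serious adverse event, due to the sponsor within 3 calendar days. Only its classification as AKI is at risk.
- *Creatinine or dialysis will usually qualify the subject.* This stands for many cases. The Section 7.5 waiver is limited to early discharges, and nothing shows that subjects with prolonged oliguria would be among them. It does not cover every case, as the check of the schedule shows.
- *The intent is plain.* The entry opens with a general concept of abruptly reduced kidney function, refers to Stage 3 and calls for staging. It was evidently not meant to exclude worse injury. A site watching in real time would also see the criterion met just after hour 6. This makes exclusion less likely, but a retrospective reader of a 14-hour episode can still exclude it on the words as printed. Saying that a 14-hour episode contains a 7-hour one leaves the upper limit with no function, in which case deleting it loses nothing.
- *AKI is not an endpoint.* This stands. Sections 5.1 and 5.2 do not include it, and Section 10.3 names no AKI analysis.

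**Conclusion.** The definition is wrong as written: its urine criterion admits oliguria of more than 6 hours and drops it again at 12 hours, and nothing elsewhere restores the longer episodes. The consequence is limited to possible misclassification. An event whose only qualifying evidence is low output for 12 hours or more can be missing from the AKI count and left unstaged, although it is still captured as an adverse event.

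The number affected cannot be derived and is probably small. The primary and secondary endpoints, the success criterion and the sample size are unaffected. The conclusion rests on a literal reading of the upper limit and on the absence of any longer band in the documents. It does not depend on the stage thresholds, which the documents do not print.

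**What to change.** In the Appendix B entry, delete the upper limit so that the urine criterion is output below 0.5 mL/kg per hour for more than 6 hours. Leave any separation by duration to the staging note. Make the same change wherever eCRF completion guidance repeats the criterion.

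The cost is a few deleted words. No assessment, visit or data item is added, and no analysis changes. The one visible effect is that the AKI count may be slightly higher.

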**Clinical Laboratory Tests:**

- White blood cell count (WBC), Hemoglobin, Platelet count
- Prothrombin Time (PT) or International Normalized Ratio (INR)
- Creatine Kinase (CK) and/or Troponins  $\leq$  72 hours before the valve implant procedure
- Creatinine (including calculation of eGFR per the Cockcroft-Gault formula)
- Albumin (as part of Frailty Index), total bilirubin
- Aspartate Aminotransferase (AST), Alanine Aminotransferase (ALT) – only for subjects with chronic liver disease
- Pregnancy test (urine or serum) – only for female subjects of childbearing potential

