### **Clinical Laboratory Tests:**

- WBC, Hgb, and platelet count
- PT or INR
- Creatinine

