**Table 3: Schedule of Assessments**

	Screening	Procedure	Post-Procedure	Discharge	30 Days	6 Months o,p	1, 3, 5 Years p	2, 4 Years o,p
Visit Window (days)	- 30 a		+ 2 n		+ 7	+ 30	+ 45	+ 45
Informed Consent	X							
Medical History	X							
Physical Assessment	X			X	X		X	
Medications: Antithrombotics	X	X	X	X	X	X	X	X
Adverse Events		X	X	X	X	X	X	X
STS Risk Score	X							
EuroSCORE II	X							
NYHA Functional Class	X			X	X		X	
12-lead ECG	X		X					
TTE	X b			X	X			
Cardiac CTA	X c							
Iliofemoral CTA	X c							
Assessment of CAD	X c,d							
Assessment of valve placement			X					
Assessment of PVL			X m					
Pulmonary Function Test	X e							
SYNTAX Score	X f							
mRS g	X							
WBC, Hgb, Platelet Count	X		X	X				
PT or INR	X		X	X				
CK and/or Troponins	X h							
eGFR	X							
Creatinine	X		X	X				
Albumin, Total Bilirubin	X							
AST/ALT	X i							
Pregnancy test	X j							
Frailty Index	X k							
Case Review	X l							
Valve Implant Procedure		X						

- a. Screening assessments will be completed within 30 days prior to valve implant procedure, unless otherwise noted.
- b. Must be performed within 90 days prior to the valve implant procedure.
- c. Must be performed within 1 year prior to the valve implant procedure.
- d. Assessment of severity of CAD may be performed by CTA or coronary angiography. If CTA shows evidence or high likelihood of obstructive CAD or if the CTA is non-diagnostic, coronary angiography must be performed to assess the need for intervention.
- e. Only for subjects with a history of lung disease.
- f. Only for subjects with significant native CAD.
- g. Every effort should be made to have a neurologist (or neurology fellow) perform the assessment. If it is not possible to have the neurologist/fellow perform the assessments within the protocol-specified visit window, a certified study team member may perform them. Following the procedure, all subjects should be assessed to determine if there is evidence of neurological impairment. For all subjects diagnosed with a new stroke after the procedure start, a follow-up mRS assessment should be performed 90 days ( $\pm$  30 days) after stroke onset to assess stroke disability (visit or phone assessment is acceptable).
- h. Required  $\leq$  72 hours before the valve implant procedure.

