
Myocardial Infarction
	
An acute ischemic event that is associated with documented and clinically significant myocardial necrosis
 
Any one of the following criteria meets the diagnosis for MI:
 
Periprocedural MI (≤ 72H after Index procedure)
 
New signs or symptoms of ischemia.
 
 
• Symptoms like chest pain or shortness of breath;
 
• Ischemic signs like ECG changes indicative of new ischemia [new ST segment elevation/depression of ≥1mm in ≥2 contiguous leads or new persistent left bundle branch block (LBBB)] or
 
• New pathological Q-waves in ≥2 contiguous leads or
 
• Imaging evidence of a new loss of viable myocardium or new wall motion abnormality
 
• AND Elevated cardiac biomarkers (Peak CK-MB rises post-procedure exceeding 5× the upper reference limit for CK-MB OR Peak troponin rises post-procedure exceeding 15× as the upper reference limit for troponin)
 
• If cardiac biomarkers are increased at baseline (>99th percentile), a further increase of at least 50% post-procedure is required AND the peak value must exceed the previously stated limit.
 
 
Spontaneous MI (Before Index Procedure or > 72 hours after the index procedure)
 
Detection of rise and/or fall of cardiac biomarkers (preferably Troponin) with at least one value above the 99th percentile URL together with at least one of the following:
 
 
• Symptoms of ischemia like chest pain or shortness of breath;
 
• ECG changes indicative of new ischemia (new ST-segment or T-wave changes or new LBBB) or new pathologic Q-waves in ≥ 2 contiguous leads
 
• Imaging evidence of a new loss of viable myocardium or new wall motion abnormality
 
 
MI associated with sudden, unexpected cardiac death
 
Sudden cardiac death or cardiac arrest, often with symptoms suggestive of myocardial ischemia, accompanied by presumably new ST-segment elevation or new LBBB, and/or evidence of fresh thrombus by coronary angiography and/or at autopsy, but death occurring before blood samples could be obtained, or at a time before the appearance of cardiac biomarkers in the blood
 
Pathologic findings of an acute myocardial infarction
	STS

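### Periprocedural MI is defined by a CK-MB or troponin peak after the procedure, but no cardiac biomarker is scheduled then and the baseline may be total CK, so MI can be classified case by case but not systematically

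*Combined protocol and SAP*

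**What the plan says.** **Definition.** The Myocardial Infarction entry in Appendix B has a category that opens "Periprocedural MI (≤ 72H after Index procedure" (closing bracket not shown). It asks for new signs or symptoms of ischemia, which may be symptoms, ECG changes or imaging findings, joined by AND to a laboratory condition: "Elevated cardiac biomarkers (Peak CK-MB rises post-procedure exceeding 5× the upper reference limit for CK-MB OR Peak troponin rises post-procedure" more than 15 times its upper reference limit. Where the baseline marker is already above the 99th percentile, "a further increase of at least 50% post-procedure is required AND the peak value must exceed the previously stated limit".

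**Before the procedure.** Section 7.2 lists "Creatine Kinase (CK) and/or Troponins". Table 3 has one row for this, "CK and/or Troponins", marked under Screening only, and its footnote h requires the test no more than "72 hours before the valve implant procedure".

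**After the procedure.** The laboratory lists in sections 7.4 (post-procedure) and 7.5 (discharge) are the same: "WBC, Hgb, and platelet count", PT or INR, and creatinine. Section 7.6 lists no laboratory test at any follow-up visit.

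**The concern.** The definition has two halves. The protocol provides for the first: every subject has an ECG after the procedure. It does not provide for the second, the biomarker peak, which becomes available only if a site chooses to test.

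The biomarker half matters because the ECG half is not specific. The qualifying ECG findings include a new, lasting left bundle branch block. Section 9.2 lists conduction system injury as a risk of the procedure, and Appendix B includes the bundle branches in its definition of a conduction defect. For such a subject the biomarker is the element that separates an infarction from an injury to the conduction system.

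The study objective in section 2 includes procedural safety, section 9.2 names infarction among the procedural risks, and there is no control arm. A low MI count that partly reflects absence of testing could be read as a property of the device.

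**Working it through.** The plan gives no MI rate, so there is no figure to reproduce. The check sets each element of the definition against the schedule.

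| Element in Appendix B | What is scheduled | Available for every subject? |
|---|---|---|
| Ischemic ECG change | 12-lead ECG at screening and post-procedure (7.2, 7.4, Table 3) | Yes |
| New wall motion abnormality | TTE at screening, discharge and 30 days (7.2, 7.5, 7.6.1) | Partly: the discharge TTE may fall inside or outside 72 hours |
| Ischemic symptoms | Adverse event capture (8.3) | By report |
| CK-MB peak above 5 times the limit | Nothing | No |
| Troponin peak above 15 times the limit | Nothing | No |
| Baseline above the 99th percentile | CK and/or troponin, up to 72 hours before | Only where troponin, or CK-MB by site choice, was measured |
| Further 50% rise | Needs the same marker before and after | No |

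**Count of scheduled cardiac biomarker tests.** Screening 1; procedure, post-procedure, discharge, 30 days, 6 months and years 1 to 5: 0. CK-MB is named at no visit. The section lists and Table 3 agree, so this is not an effect of a broken table.

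**Total CK as baseline.** Appendix A lists CK and CKMB as separate terms. A site that measures only total CK has met section 7.2, but has no baseline for either marker in the definition. For that subject the 50% rise rule cannot be evaluated, even if troponin is drawn later on suspicion.

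**Other routes to MI within 72 hours.** The spontaneous category covers only events before the procedure or more than 72 hours after it. The sudden-death category requires a death, and the last category requires pathologic findings. Neither of these two needs a biomarker. For a subject who survives the window, the periprocedural category is therefore the only clinical route, and it is closed without a test.

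**Size.** One subject among the planned maximum of 110 is 1/110 = 0.9 percentage points. Assume, for illustration only, a true periprocedural MI rate of 1% to 3%: 0.01 × 110 = 1.1 and 0.03 × 110 = 3.3 subjects. If a share *s* of true cases has the right marker drawn, at most *s* × rate can be classified:

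- *s* = 1: 1% to 3%
- *s* = 0.5: 0.5% to 1.5%
- *s* = 0: 0%

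The documents fix neither the rate nor *s*. Because *s* is set by site habit, it can differ across the up to 8 sites.

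**The case against.** The case on the other side has five parts.

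- **Appendix B classifies events; it is not a test schedule.** Hemolysis, for example, rests on blood tests and a hematologist's confirmation that are not scheduled either, and work-up triggered by an event is a normal model. This stands, and it is why reporting MI as clinically detected is an acceptable solution. It does not explain the total CK baseline, which was scheduled and does not match the definition. Acute kidney injury shows the contrast: it rests on change in creatinine, which is measured at screening, post-procedure and discharge.
- **The definition also needs a sign or symptom.** Testing everyone would change the classification only of subjects who already have one. This stands and narrows the gap: nothing obliges a site to draw a marker once a sign appears.
- **The baseline draw has some use.** A troponin baseline serves any later troponin drawn on suspicion, and the test may bear on exclusion 8 (recent MI), although the protocol does not state that purpose. This stands. A reader might infer that the draw is worthless; that is true only of the 50% rule in subjects with total CK alone.
- **The direction of error is not certain.** Applied strictly, the definition can only miss untested survivors. But section 8.3 has adverse events recorded by diagnosis. The sponsor review described there covers relatedness, anticipation and seriousness and does not mention a check against Appendix B. An untested ECG-only case could therefore also be recorded as MI. A reader might infer a rate that is certainly too low; the documents support only incomplete, site-dependent ascertainment.
- **One extra sample would not establish a peak.** Section 7.4 covers 48 hours, the MI window is 72 hours, no sampling time is given, and subjects discharged within 48 hours need not repeat laboratory tests. This stands, and the fix has to say so.

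**Conclusion.** The definition and the schedule do not fit together. The definition needs a CK-MB or troponin value after the procedure, the protocol schedules none, and its baseline requirement can be met by a marker that the definition does not use. Periprocedural MI can be classified where a site tests, but not systematically, and an untested survivor cannot qualify.

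Two stronger readings are tempting. The first is that no biomarker is ever drawn and the definition cannot be applied at all. The documents show only that none is required; nothing prevents a site from testing. The second is that the trial's conclusion is at risk. MI appears in neither section 5.1 nor section 5.2, so the success criterion and the sample size are untouched. What is affected is the descriptive reporting in section 10.3, including any Kaplan-Meier estimate for MI.

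The size is modest: 0.9 percentage points per subject, and about 1 to 3 subjects in all under the assumed 1% to 3% rate. The conclusion that ascertainment is incomplete rests on the assumption that not every site tests every subject who has a sign or symptom. The mismatch itself rests on no assumption. It is worth correcting because the first step costs almost nothing.

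**What to change.** 1. **Baseline.** In section 7.2 and Table 3, replace "CK and/or Troponins" with CK-MB and/or troponin, so that the baseline marker is one that the definition uses. The cost is negligible: the draw already takes place.

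2. **After the procedure.** Reconcile Appendix B with sections 7.4 and 7.5 in one of two ways.
   - Add the same assay as at baseline to the blood sample already scheduled in section 7.4, at a stated time, and mark it in Table 3. The cost is one added analyte and some elevations without clinical consequence, which the requirement for a sign or symptom keeps from counting as MI. A single sample may miss the peak, so a value below the limit would not exclude MI.
   - Leave the schedule as it is and report periprocedural MI as *clinically detected*, together with the number of subjects who had CK-MB or troponin measured within 72 hours. Do not present it as a systematically ascertained rate under the Appendix B definition. This needs no new testing, only a record of who was tested and one sentence in section 10.3.
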